2.1 Background

In Veterans, chronic pain and prescription opioid use are strongly associated with mental health problems. Veterans with chronic pain and comorbid mental health conditions experience greater pain severity and more pain catastrophizing than those with chronic pain alone. The higher prevalence of opioid use among patients with chronic pain and mental health problems may be driven, in part, by a desire to alleviate mental health symptoms. Prescribing opioids in the context of chronic pain and mental health conditions can exacerbate both mental health and chronic pain conditions, worsen psychosocial functioning, increase risk for serious adverse medical events, and culminate in breakdowns in patient and provider communication and trust.¹⁻³

Currently, there is little evidence that opioids are effective in the long-term treatment of chronic pain; furthermore, they can result in poorer quality of life and serious adverse outcomes. Evidence suggests Veterans may be disproportionately affected by opioid-related harms; VA patients have nearly twice the rate of accidental poisoning deaths as US adults overall and opioid analgesics are the drug class most commonly involved in these deaths.⁴ In short, the expansion of opioid prescribing has triggered an epidemic of opioid-related deaths and addictive disorders without reducing the burden of pain or improving patients' functioning and quality of life.

Concurrently, the opioid crisis has led to a breakdown in primary care management of chronic pain that has negatively impacted both patients and providers. New national guidelines and policies intended to reduce harms from opioids have put pressure on health care systems to change their approach to pain management. The medical community has responded with attempts to rein in the use of opioids,⁵ leaving many patients who have relied on opioids in need of effective alternatives. Unfortunately, numerous barriers limit effective pain management in primary care, including ineffective communication, patient and provider knowledge deficits, limited time, and insufficient access to information, assessment tools, and treatment pathways. Healthcare systems lack guidance and resources for implementing effective systems of chronic pain care with primary care. This study specifically addresses these health services gaps.

Newer research suggests that multi-modal and integrated pain care that incorporates non-pharmacological modalities such as exercise, physical therapy, behavioral health care, social supports, and self-care strategies can be more effective than medication-based therapies alone. Despite high-level recommendations for biopsychological pain management, little to no evidence is available for specific strategies to taper or replace opioid therapy and to promote a primary care-based, multi-modal, non-pharmacological approach to chronic pain care.⁶ We posit that the VA's patient-centered Whole Health Model can help guide the implementation of multi-modal pain care for Veterans in primary care. The comparator intervention that will be tested in this trial – Primary Care-Group Education – is an adapted version of Cognitive Behavioral Therapy for Chronic Pain (CBT-CP) delivered in a group format in primary care. Both interventions will be compared to usual primary care.

2.2 Study Objectives

1. Conduct a multi-site, pragmatic randomized clinical trial to compare two health care delivery approaches for chronic pain management-Whole Health Team (WHT) and Primary Care Group Education

(PC-GE), and both will be compared to Usual Primary Care (UPC) in veterans with moderate to severe chronic pain.

2.3 Specific Aims

Aim 1: Conduct a multi-site pragmatic trial of Whole Health Team (WHT) vs. Primary Care Group Education (PC-GE) and both compared to Usual Primary Care in veterans with moderate to severe chronic pain. We hypothesize that WHT will be superior to PC-GE, and both will be superior to Usual Primary Care (UPC) with respect to the following outcomes:

H1.a. Improved pain interference at 12 months (primary outcome) and pain intensity, functioning, and quality of life (secondary outcomes).

H1.b. Decreased use of higher-risk pain medications, including opioids or high-risk combinations of pain medications (i.e., co-prescription of opioids and benzodiazepines) (secondary).

H1.c. Engagement in a greater number of non-pharmacological pain management activities (secondary).

H1.d. Improvement in mental health-related symptoms, including sleep problems and suicidality (secondary).

1. Randomization

The unit of randomization was the individual. Stratified block randomization with varying block sizes (24 or 48) was used. Participants were stratified by site, sex, and current opioid therapy and were randomized in an 11:11:2 (WHT:PC-GE:UPC) ratio. Allocation concealment was maintained through a module in Stata called "RALLOC".

2. Blinding

It is not possible to blind participants or those delivering the intervention to treatment assignment. However, we have blinded the study statistician, the PIs of the study, and those assessing patient reported outcomes will be blinded.

3. Outcomes

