After electronic signature of the IC has been verified or study staff receive a copy of the signed informed consent via mail, and after completion of the baseline assessment, participants who remain study-eligible will be officially enrolled and randomized to one of the three study arms. The study staff will then provide a comprehensive orientation to the study arm to which they were assigned either at the end of the baseline call or at another scheduled telephone appointment, depending on patient preference.

We will perform stratified random allocation with a blocked randomization scheme that includes varying block sizes of 24 and 48. We plan to stratify by site, gender and current opioid therapy, which will yield 24 strata (=6 sites x 2 genders x 2 levels of current opioid therapy). Randomization will be carried out within the strata, ensuring that the main covariates are balanced across treatments. The blocking technique helps ensure a constant ratio of treatment allocations maintained throughout the randomization period. To assist concealing the pattern of blocks, we will randomly order the blocks of different sizes. We will use a Stata Module called “RALLOC” (Ryan, 1997) to perform the random allocation. This program saves the allocation sequence into user-defined Stata files and helps ensure that a record is kept of the randomization protocol.

Finally, the study staff will then provide a comprehensive orientation to the study arm the patient was assigned to either at the end of the baseline call or at another scheduled telephone appointment, depending on patient preference. Participants randomized to the WHT and PC-GE arms will also receive a patient binder (electronically through encrypted email or hard copy) containing intervention-related documents to help reinforce topics covered.

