## 8.0 Statistical Considerations

### 8.1 General Design Issues

We hypothesize that WHT will be superior to PC-GE and both will be superior to Usual Primary Care in improving pain interference (primary hypothesis), pain intensity, functioning and quality of life, decreasing use of high-risk pain medications, promoting engagement of non-pharmacological pain management activities, and improving mental health symptoms (secondary hypotheses).

Our trial design is individual randomization because the interventions are delivered at the individual level, although the PC-GE intervention is performed in a group format. Even in this group-format intervention, therapists may rotate over time, so there is no consistent cluster effect measured by the intra-class correlation coefficient. Furthermore, we are interested in outcomes measured at the patient-level rather than the aggregate group level.

Before randomizing individual patients into 3 arms, we will construct strata based on prognostic variables including site, sex, and opioid use. This stratified randomization approach helps ensure balance of the treatment groups with respect to the combinations of the prognostic variables. We will use permuted blocks of sizes 3, 6, or 9 within each stratum to achieve balance.

The total Brief Pain Inventory (BPI) interference sub-scale score is our primary outcome measure. The BPI interference subscale includes seven numeric ratings of pain interference with general activity, mood, walking, work, relations with other people, sleep, and enjoyment of life and is scored as the average of the individual item scores. We will also report scores of the total BPI and BPI intensity. The BPI is a multidimensional measure that has been validated for use in numerous populations, including primary care patients with chronic pain, and is responsive to change.

Past-year use of complementary therapies and self-management practices will be measured using the Nonpharmacological and Self-Care Approaches from PMC (NSCAP). The inventory assesses use of several CIH modalities such as yoga, etc. We will also probe for other self-directed pain management activities.

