## 8.2 Sample Size and Randomization

### Sample Size

The sample size calculation was based on the BPI interference sub-scale (primary outcome), which is calculated by summing 7 item scores and dividing by the number of items without missing values. Based on repeated-measures ANOVA, using the F test, we focused on 2 types of pair-wise comparisons:

1. Two active interventions compared with each other: WHT vs. PC-GE.
2. Two active interventions respectively compared with Usual Primary Care (UPC): WHT vs. UPC and PC-GE vs. UPC.

For the 1st pair-wise comparison, we used an alpha of 0.03 and effect size (between-group) of 0.15. For the 2nd pair-wise comparison, we used an alpha of 0.01 and effect size of 0.30. The final family-wise error rate is 0.05 (0.03+0.01+0.01). We assumed a power of 0.9 and two-repeated measures, and an equal allocation (ratio 1:1) for the first pair-wise comparison. Given the sample sizes for the 2 active arms calculated in the first step, we assumed an unequal allocation ratio when computing sample size for the UPC arm in the 2nd pair-wise comparison. We used our prior OPTI study data for this computation: the correlation between repeated measures is 0.66 and the variance is 5.90 (assuming stays constant over time). Using these prior data, we determined a sample size of 273 per arm for the 1st pair-wise comparison, and 50 for the UPC arm in the 2nd pair-wise comparison. Allowing for a 20% attrition rate, the final sample size is 765 (83 in the UPC arm, 341 in the PC-GE arm and 341 in the WH arm). Based on prior similar studies, we anticipate that at a minimum, 70% screened will be eligible to participate and of those eligible, roughly 20% will enroll. If we require approximately 765 patients to complete to test the primary study hypothesis, we would therefore need roughly 3,825 eligible patients, and would need to screen 5,464 patients.

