### Randomization

After obtaining written consent and completing the baseline interview, the local site coordinator will initiate randomization using the study application randomization form. For those who sign the IC document and mail back the forms, the study coordinator will wait until the written consent form is received before randomizing the patient to a study arms. The randomization code will not be visible to personnel conducting randomization and can be completed only once per study ID, preventing study personnel from influencing treatment allocation. This process will simultaneously inform the coordinator and participant of the primary study arm assignment.

- The unit of randomization is the patient. After eligible and interested patients complete a written informed consent, each site will randomize enrolled patients to WHT, PC-GE, or

Usual Primary Care in permuted blocks of 24 and 48, stratified by site, prescription opioid use (yes/no) and sex. We will oversample women veterans, aiming for roughly 20% at each site. Because the sample size computation was based on 2 types of pairwise comparisons with different pre-specified effect sizes and alpha levels, the numbers of patients are different across intervention arms. The enrollment period is approximately 24-30 months: The target enrollment for each site is 17 patients in the UPC arm, 69 in the WHT arm and 69 in the PC-GE arm over the duration of the enrollment period.

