Objectives	Conduct a multi-site, pragmatic randomized clinical trial to compare two health care delivery approaches for chronic pain management (Whole Health Team (WHT) and Primary Care Group Education (PC-GE)) and both compared to Usual Primary Care (UPC) in veterans with moderate to severe chronic pain.
Number of Participants	Planned 765; actual 769
Main Inclusion Criteria	Assigned to VA primary care physician; report pain every day or nearly every day for ≥ 6 months using a phone eligibility screener; PEG score of ≥ 4 .
Intervention(s)	
The more intensive WHT model is delivered by an interdisciplinary pain team consisting of a primary care provider (PCP), integrative health clinician (e.g. mindfulness instructor). The WHT will use the VA Whole Health Personalized Health Planning and Coaching model to promote wellness in veterans with chronic pain.
 
The less resource-intensive, PC-GE, uses an abbreviated Cognitive Behavioral Therapy for Chronic Pain (CBT-CP) manualized therapy adapted for a group format based in primary care. This model consists of 7 psychologist-led weekly group sessions emphasizing pain self-management skills and various multi-modal non-pharmacologic approaches for chronic pain management.
 
Both interventions will be compared to Usual Primary Care in which enrolled patients with chronic pain will be randomized to receive usual primary care. Usual primary care incorporates the VA Stepped Care Model for Pain Care which encourages referrals from primary care for secondary and tertiary pain care services, as well as use of Whole Health and complementary and integrative health (CIH) services for pain.

Duration of Intervention and Follow-up	12-months
Blinding	Study statistician; PIs; assessors
Primary Outcome	Pain interference score measured using the Brief Pain Inventory (BPI) interference subscale at 12 months.
Primary Analysis	Hierarchical multi-level model, adjusting for baseline value of the outcome and stratification variables, i.e., site, gender, and current opioid therapy, accounting for repeated measures of individuals and individuals nested within treatment. Pairwise comparisons will be made.

Key Secondary Outcomes	Pain intensity; functioning; quality of life; use of higher-risk pain medications; engagement in non-pharmacological pain management activities.

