The primary outcome is change in BPI interference from baseline to 12-months. Sample size estimates were based on repeated-measures ANOVA assuming two-repeated measures, using the F-test with a focus on the pairwise comparisons. The overall family-wise type I error rate was set at 0.05 with a split of 0.03 for the WHT vs. PC-GE comparison, 0.01 for the WHT vs. UPC comparison and 0.01 for the PC-GE vs. UPC comparison. We assumed a power of 90% for all comparisons. For the comparison between WHT and PC-GE we assumed 1:1 randomization and an effect size of 0.15, which was informed by our prior OPTI study where the correlation between repeated measures was 0.66 and the variance (assuming constant over time) was 5.9. With these assumptions, we determine we would need a sample

size of 273 per arm in the WHT and PC-GE arms. Given the sample size of 273, and assuming an effect size of 0.3, we determine the sample size (using an unequal allocation) needed for the UPC arm to be 50. Assuming a 20% attrition rate, the final sample size was 765 (341 in each of the WHT and PC-GE arms and 83 in the UPC arm).

5. Interim Monitoring

Interim monitoring will focus on patient accrual, baseline comparability of treatment groups, protocol adherence, loss to follow-up, data completeness, quality, and safety. No formal interim look for effectiveness or futility are planned.

6. Data Collection and Data Freeze

Data will be collected using REDCap through primary data collection of patient-reported outcomes. We will use the VHA electronic health record (EHR) to capture selected outcome measures from VA clinical visits (e.g. medications).

Data will be locked one month prior to meeting with the DSMB so that reports can be prepared and distributed to members. The final data set will be locked before conducting any of the proposed analyses.

7. Analytic Plan

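### The 11:11:2 allocation and the 341/341/83 sample size are incompatible, and the 83 for Usual Primary Care does not follow from the plan's own attrition step

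*SAP*

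**What the plan says.** - **Ratio.** The SAP's Randomization section says participants "were randomized in an 11:11:2 (WHT:PC-GE:UPC) ratio".
- **Blocks.** The same section says "Stratified block randomization with varying block sizes (24 or 48) was used". Protocol 8.2 (Randomization) agrees: "Usual Primary Care in permuted blocks of 24 and 48". Protocol 7.2.2 gives the same sizes over strata defined by site, sex and opioid therapy, "which will yield 24 strata (=6 sites x 2 genders x 2 levels of current opioid therapy". Protocol 8.1, also current text, says instead: "We will use permuted blocks of sizes 3, 6, or 9 within each stratum to achieve balance".
- **Arm sizes.** The SAP's Sample Size section says "the final sample size was 765 (341 in each of the WHT and PC-GE arms and 83 in the UPC arm". The Precis and Protocol 5.3 and 8.2 give the same split.
- **Derivation.** For the two active arms, Protocol 8.2 says "we determined a sample size of 273 per arm". It then gives 50 for UPC and allows for 20% attrition. The SAP repeats these inputs.
- **Site targets.** Protocol 8.2 gives 69 WHT, 69 PC-GE and 17 UPC per site. Protocol 5.3 gives the same figures as averages over the initial five sites.
- **Total.** The SAP synopsis gives "Planned 765; actual 769". Neither document reports the numbers randomised per arm.

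**The concern.** UPC enters two of the three primary comparisons and is by far the smallest arm, so its size governs their precision. A reader who takes 83 from the sample-size section will expect tighter UPC contrasts than 11:11:2 can deliver. Conversely, if about 83 were in fact randomised to UPC, the ratio cannot have been a constant 11:11:2, and the analysis model would need to reflect how allocation was done. The two block schemes raise the same question, because a scheme with blocks of 3 cannot have used 11:11:2. The primary model in SAP 7.2 adjusts for baseline BPI interference, site, gender and opioid therapy. It has no term for enrolment or allocation period.

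**Working it through.** **1. Attrition step.** Inputs: 273 evaluable per active arm, 50 evaluable in UPC, 20% attrition (Protocol 8.2, SAP Sample Size). Formula: n/(1 − 0.20).
- Active arms: 273/0.8 = 341.25, so the stated 341 reproduces.
- UPC: 50/0.8 = 62.5, so 63. The stated 83 does not reproduce.
- Total: 341 + 341 + 63 = 745, not 765. The excess is 20, which is exactly 83 − 63.
- Working back from 83: 83 × 0.8 = 66.4. Likewise the 612 subjects with outcomes in the Protocol's Missing Data section equal 765 × 0.8, and 612 − 2 × 273 = 66. Both imply 66 evaluable UPC patients, where the calculation gives 50.

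**2. Allocation step.** The UPC share is 2/24 and each active share is 11/24.

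| Total | WHT | PC-GE | UPC |
|---|---|---|---|
| 745 | 341.5 | 341.5 | 62.1 |
| 765 | 350.6 | 350.6 | 63.8 |
| 769 | 352.5 | 352.5 | 64.1 |

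The ratio therefore matches 341/341/63, the split that does follow from step 1. The stated split corresponds to 341/765 × 24 = 10.7 and 83/765 × 24 = 2.6 per block of 24. The site targets carry the same error: at 11:11:2, 69 per active arm goes with 69 × 2/11 = 12.5 in UPC, not 17.

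**3. Incomplete blocks.** These were simulated over 24 strata with N = 769 and blocks of 24 and 48 equally likely. The documents do not give stratum proportions, so equal sites, 20% women and 30% on opioids were assumed. Mean UPC was 64.0 (SD 3.6), with a 99% range of 54 to 73. None of 5,000 runs reached 83.

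**4. Block sizes.** The smallest block that carries 11:11:2 is 24. Blocks of 3, 6 or 9 cannot.

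**5. Precision.** The formula for the difference detectable with 90% power at two-sided alpha 0.01, single-measure basis, is (2.576 + 1.282) × SD × √(1/n1 + 1/n2), with SD = √5.90 = 2.43.
- 273 vs 66 (from 83 randomised): 1.29 points
- 282 vs 51 (from 352 and 64 randomised): 1.43 points
- 273 vs 50 (the plan's own evaluable numbers): 1.44 points

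**6. Power at the assumed effect size.** The 0.30 is read as Cohen's f, the reading under which 50 reproduces on a single-measure basis. At alpha 0.01, 282 vs 51 gives 91.2% (one measure) or 95.9% (two measures, correlation 0.66). For 273 vs 66 the figures are 96.3% and 98.7%.

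**7. If the ratio changed (assumption only).** Let x participants be randomised early with UPC share s, and the rest at 11:11:2. Reaching 83 of 765 needs x = (83 − 63.75)/(s − 1/12). The last column is the shift in an unadjusted UPC contrast for each 1-point early-to-late drift in the outcome, that is, the difference between the two early shares.

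| Assumed early ratio | x | Early share of UPC | Early share of each active arm | Shift |
|---|---|---|---|---|
| 1:1:1 | 77 | 31% | 7.5% | 0.23 |
| 2:2:1 | 165 | 40% | 19% | 0.20 |
| 4:4:1 | 693 | 93% | 90% | 0.02 |

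**The case against.** The strongest reply is that 341/341/83 is a prospective calculation, not a report of allocation, and that nothing was lost. This largely stands. The ratio agrees with the 50 evaluable patients that the power calculation calls for, and only the 83 stands apart. Applied to 612 evaluable subjects, 11:11:2 gives 280.5/280.5/51, which meets 273/273/50. It does not remove the contradiction, because both figures are stated as the design and no reason for 83 is given.

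Two stronger readings are tempting.

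- **A reader might infer that UPC is about 23% too small and the comparisons underpowered.** The 23% is measured from 83, which the plan never needed. Single-measure power for a 1-point difference does fall from 66% (273 vs 66) to 55% (282 vs 51). At the plan's own 273 vs 50 it is already 54%: 1/(2.43 × √(1/273 + 1/50)) = 2.68, less 2.576. The 1-point threshold appears only in the exploratory responder analysis and is not the sample-size effect.
- **A reader might infer that the trial began at 1:1:1 and switched, so that the UPC contrasts are confounded with calendar time.** There are hints. Protocol 8.1 keeps blocks of 3, 6 or 9, and a block of 3 fits three arms in a fixed ratio only at 1:1:1. The revision history puts the rise from 745 to 765 and the change to blocks of 24 and 48 in the same version. But no passage states an earlier ratio, a change of ratio or a count at a switch, and solving one unknown to reach 83 is not evidence. Adjustment for baseline BPI and site would absorb some drift. SAP 7.4 also examines time periods, though only as exploratory analysis.

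**Conclusion.** The point holds as a contradiction in the stated design. A constant 11:11:2 gives about 64 in UPC, not 83, and chance in incomplete blocks is not a credible explanation under the stratum proportions assumed. The 83 also fails the plan's own step (63), and Protocol 8.1 contradicts the block sizes given elsewhere. Planned power for the UPC comparisons is not lost, taking 50 evaluable as the requirement and 20% attrition as realised. The error lies in the stated UPC size and the precision a reader would take from it: 1.43 rather than 1.29 BPI points.

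Confounding with calendar time is a possibility that the documents leave open, not a finding. It would need both a change of ratio and a drift in outcome. Its size cannot be determined from the documents: about 0.02 to 0.23 points per 1-point drift under the early ratios assumed above, before covariate adjustment.

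**What to change.** 1. **Planned sizes.** In the Precis, Protocol 5.3 and 8.2, and the SAP's Sample Size section, make the planned UPC figure and total agree with 50/0.8 and 11:11:2. That means 341/341/63 = 745 as the required size or, if 765 is kept as the recruitment target, about 351/351/64. Otherwise state why 83 was chosen. Align the 612 in the Missing Data section: 2 × 273 + 50 = 596 is what the calculation requires. Keep these as planned figures and report the numbers actually randomised per arm separately.
2. **Block sizes and site targets.** Correct the block sizes in Protocol 8.1 and the 69/69/17 site targets in 8.2 and 5.3, stating how many sites the targets are divided over.
3. **Allocation history.** State in the SAP, before unblinding, whether the ratio or the block scheme changed during enrolment, and when. Only if the ratio changed, add allocation period (before/after) as a fixed effect in the primary and secondary models.

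Items 1 and 2 are wording changes. Item 3 is one sentence and, if needed, one covariate that can be taken from the randomisation records. The SAP allows modification until final data lock and before unblinding. A period term added later would look post hoc. The only other cost is that the stated UPC precision becomes slightly less favourable.
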